11.1. Risk Level (According to Resolution 8430)

This study complies with the CIOMS declarations, international human research agreements such as the Helsinki declaration and the Nuremberg code, and the national regulations of article 11 of resolution 8430 of 1993, It is considered a study with risk "greater than the minimum", since it is a study where two surgical interventions will be randomized. However, these interventions are part of the conventional and accepted therapeutic options for the management of PAS. Given the implicit risk of this study, informed consent will be requested from all patients prior to undergoing any intervention.

To ensure the confidentiality of the data, the identification variables of each patient will be coded to prevent the traceability of the identification; no one outside the research group or the ethics committee will have access to the database, and no data will be published that would allow the identification of the participants.

Before the start of the study, the approval of the ethics committee will be requested for the study protocol, the informed consent forms, and the declaration of the mother head of the household.

Substantial amendments that require review by the ethics committee will not be implemented until the committee provides a favorable opinion for the trial.

Informed consents obtained from randomized patients will be notified monthly to the ethics committee for review. The inclusion of the first participant will be notified to the committee within the first 24 hours after signing the informed consent. A semiannual report on the progress of the study will be made or sooner if this is required

The principal investigator will notify the ethics committee of the end of the study. If it is terminated prematurely, the committee will be notified explaining the reasons for the premature termination.

11.2. Consent:

According to resolution 8430 of 1993, article 14, for research on human beings, there will be written informed consent, by which the research subject or their legal representative understands and accepts their consent (Appendix 7).

To obtain informed consent to the legal representative, the following information will be provided

- a) Purpose of the investigation and procedures
- b) Study inclusion criteria and time of participation
- c) Risks and benefits
- d) Confidentiality of information
- e) Payments and compensation

Informed consent will be obtained before the participant undergoing any trial-related intervention. Because this study considers a vulnerable population (pregnant women) as the reference population, the informed consent is based on resolution 8430, article 30, where it is contemplated that the informed consent of the woman and her spouse must be obtained, prior information from the possible risks for the embryo, fetus or newborn in your case. If informed consent cannot be obtained from the spouse, there will be a statement from the mother head of the family where the study participant certifies that she is economically and socially responsible for her minor children (Appendix 8).

The principal investigator retains overall responsibility for conducting research on his site, this includes obtaining informed consent from participants on his site. They must ensure that any person to whom the responsibility of participating in the informed consent process is delegated is duly authorized, trained, and competent to participate in accordance with the ethically approved protocol, the principles of Good Clinical Practice (GCP), and the Declaration of Helsinki. If a delegation of consent is acceptable, details must be provided.

The participant will remain free to withdraw at any time from the trial without giving reasons and without jeopardizing her further treatment and will be provided with a point of contact where she can obtain further information about the trial. The data collected up to the time of withdrawal will only be used after withdrawal if the participant has consented to it. Any intention to use such data will be described in the consent literature. When a participant is required to give her consent again or a participant is required to provide new information, it will be the responsibility of the principal investigator to ensure that this is done promptly.

The Principal Investigator at each site assumes responsibility for ensuring that all vulnerable participants are protected and voluntarily participate in an environment free from coercion or undue influence.

Consent will include the use of anonymous images (ultrasound or MRI), photographic and video recording of operative findings, as well as histopathology slides for independent review by blind experts.

11.3. Conflict of interests

The researchers of this study declare that they have no conflicts of interest.

12. Report of adverse events:

The principal investigator of each center will be responsible for managing the safety of each participant and identifying adverse events related or not to the study interventions.

Adverse events should be recorded with the following information:

- Identification of the participant in the study.
- Time from randomization to occurrence of the event.
- Identification of the possible causal relationship between the event and the surgical intervention (hysterectomy or partial myometrial resection)
- Resolution or improvement of the adverse event.

12.1. Monitoring of adverse events:

All adverse events (AE) that occur within the first 42 days after randomization must be reported to the respective ethics committee following the guidelines for reporting serious adverse events (SAE), maintaining the confidentiality of the information. The SAE must be reported to the committee within the first 24 hours of the event.

12.2. Definition of adverse event: An Adverse Event (AE) is considered to be any adverse medical situation in a patient or subject of a clinical investigation who was

administered a pharmaceutical product or underwent a procedure and that does not necessarily have a causal relationship with this treatment. Therefore, an AE can be any unfavorable or unintended sign (including an abnormal laboratory finding), symptom or disease temporarily associated with the use of a medicinal product (research) or a certain intervention, whether or not it is related to it. product or intervention.

- Events that meet the definition of EA and their expected frequencies:
- Transfusions of more than 4 units of red blood cells (UGR):> 40%
- Bladder injury:> 60%
- Ureteral injury:> 30%
- Surgical wound infection:> 30%
- Complications related to intra-arterial balloons such as vessel thrombosis:> 30%

Events that DO NOT meet the definition of EA:

- Post-operative ileus
- Urinary retention
- Supra fascial hematoma
- Postpartum hemorrhage <2.5 L
- Expected daily fluctuations of pre-existing diseases or conditions present or detected at the beginning of the study that do not worsen.

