9.8. General flowchart of study

9.9. Randomization flowchart

9.10. Procedures flowchart

Visit number	V1	V2	V3	V4	V5	Vn
Day	D0	D1	Hasta 72h Postoperatori as	D7 a D12 Postoperator io	D42 Postoperator io	Visitas no programad as
Name of the visit	Selecció n	Aleatorizaci ón	Seguimiento 1	Seguimiento 2	Fin de Seguimiento	Seguimient o N
Activity						
Hospital admission	Х					Х
Inclusion and exclusion criteria	Х	Х				
Assignment of consecutive number (Screening)	Х					
Informed consent	X					
Demographic data	Х	Х				

Obstetrics						
and	Х	Х				
history						
Short						
Physical						
Examination		Х				
(Height and						
weight)						
Laparotomy /		v				
on		Λ				
Hydrostatic						
balloon						
uterine		Х	Х			
tamponade						
Characteristi						
cs of the		Х				
surgical						
Nouthorn						
vital status		v	x			
and weight		71	7			
Type of						
postoperative			V			
hospitalizatio			А			
n						
Complication			x	x	x	x
of surgery						
ICU			х	Х	х	х
admission						
Surgical			V	V	V	V
reinterventio			Х	Х	Х	Х
discharge			Х	Х	Х	Х
Evaluation						
Near Miss			x	х	х	х
Criteria						
Blood						
component			x	х	х	х
transfusion						
Arterial						
thrombosis						
associated			Х	Х	Х	Х
with vascular						
intervention						
11			77			
lleum			Х			
Supra fascial						
hematoma			Х			
Surgical						
wound				Х	Х	Х
infection						

Clavien Dindo Scale		Х	Х	Х	Х
Hospital discharge			Х	Х	Х
Adverse Events	Х	Х	Х	Х	Х
Telephone contact (Telemedicin e)				Х	

9.11. Operative aspects:

Eligible women will receive complete information about the study. If they agree to participate in it, they will sign the informed consent for both interventions: hysterectomy and partial myometrial resection. The final modality of intervention will be decided at randomization prior to the start of the surgical procedure.

The patients will undergo laparotomy with adequate anesthesia, the anesthesia method will be decided based on the pre-anesthetic evaluation and the mother's choice. During laparotomy, the clinical signs and the FIGO classification for PAS will be recorded¹⁷: Once the abdomen is surgically entered, the anterior aspect of the uterine segment is observed in detail (it is likely that a vesicouterine dissection will be required) and the diagnosis of PAS is confirmed (See Appendix 2, Definition of confirmed case of PAS).

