- **10.2.1. Intraoperative**: The total intraoperative bleeding volume will be measured, type of anesthesia used, type of skin incision, type of uterine incision, FIGO PAS classification, use of interventional radiology, use of intraoperative cell saver ("cell saver"), duration of surgery, use of uterine tamponade with hydrostatic balloons, gender and weight of the newborn.
- 10.2.2. **Immediate post-operatory time**: defined as the first 48 to 72 hours after the intervention, in this period of time, the patient will be monitored in the obstetric gynecological service, where each of the secondary outcomes described will be evaluated: Maternal death, Presence of Near Miss criteria, frequency and volume of transfusion of blood components, bladder injury, ureteral injury, need for reoperation, admission to ICU, days of postoperative hospital stay, disseminated intravascular coagulation, hypovolemic shock, metabolic acidosis, urinary retention, femoral thrombosis, post-operative ileus, supra fascial hematoma.
- 10.2.3. **Medical appointment between 7 and 12 days:** The patient is clinically evaluated by outpatient consultation on-site or telemedicine with the treating physician who determines if any of the secondary outcomes described above have occurred and additionally if she has developed an infection of the surgical wound.
- 10.2.4. **Follow-up at 42 days postpartum:** the patient will be followed up by telephone when she reaches 42 days after the surgical intervention, where a general evaluation of her health will be made, and the follow-up will be terminated.

10.3.Data quality monitoring:

Both the executing institution and the institutions participating in the study will designate a person in charge of monitoring the quality of the data. In the executing institution, the person in charge will be [name], who will perform a data quality analysis of 100% of the data corresponding to the primary outcome to be evaluated and 100% for the secondary outcomes, in this analysis of quality, a review of the data entered into the system will be carried out and it will be compared with the clinical records of each institution, the process will be carried permanent and will be programed the first monitoring with each center 5 days after to first participant enrollment, the additional monitoring visits will be performed according to recruitment rate and presence of primary and secondary outcomes in participating individuals.

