12.3. Definition of serious adverse event (SAE)

Serious adverse event (SAE) is defined as any unfavorable occurrence that has the following characteristics:

- Cause death
- Life-threatening: "Life-threatening" corresponds to situations in which the participant was at risk of death at the time of the event.
- Requires hospitalization (hospital admission for constant observation or prolongs existing hospitalization)
- Causes a significant disability or alteration of a person to perform normal vital functions, persistent or significant disability, does not include events of minor significance such as common headache, nausea, vomiting, diarrhea, flu, accidental trauma that may interfere with normal functions of everyday life and prevent them, but they are not important events.
- Congenital anomaly / birth defect in the participant's offspring.

• Major medical events at the discretion of the principal investigator that may endanger the participant.

12.4.EA and SAE registration:

- The investigator will review all the documentation related to the adverse event and verify that it is consigned in the adverse event report form (Appendix 6).
- The investigator will determine a diagnosis based on symptoms, signs, and all clinical information. The diagnosis is the one that is recorded as an adverse event.
- In the event of serious adverse events, the principal investigator will report them to the institutional ethics committee within the first 24 hours of detecting the adverse event.
- In case of adverse events, the principal investigator will report it to the institutional ethics committee within the first month of detecting the adverse event.

12.5. Assessment of AE intensity:

The researcher will carry out an evaluation of the intensity of each AE and SAE:

Grade 1 or mild: Mild symptoms that cause minimal or no interference with social activities and usual functions with indicated intervention.

Grade 2 or moderate event: Moderate symptoms causing more than minimal interference with usual social and functional activities with indicated intervention.

Grade 3 or serious event: Serious symptoms that cause inability to perform usual social and functional activities with indicated intervention or hospitalization.

Grade 4 or life-threatening event: possibly life-threatening symptoms causing inability to perform basic self-care functions with indicated intervention to prevent permanent failure or ongoing disability or death.

Grade 5 death related to AE.

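### Section 12.2 excludes four complications from adverse-event status without a seriousness proviso, contradicting 12.3, and the flowchart and 10.2.3 disagree on how long ileus and suprafascial haematoma are collected

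*Combined protocol and SAP*

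**What the plan says.** **Adverse-event definition (section 12.2).** The general definition is broad: "an AE can be any unfavorable or unintended sign (including an abnormal laboratory finding), symptom or disease" associated in time with an intervention, whether or not related to it. The same section then has a list headed "Events that DO NOT meet the definition of EA". It contains post-operative ileus, urinary retention, suprafascial haematoma and "Postpartum hemorrhage <2.5 L". A fifth item reads "Expected daily fluctuations of pre-existing diseases or conditions present or detected at the beginning of the study that do not worsen".

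**Serious adverse events (section 12.3).** "Serious adverse event (SAE) is defined as any unfavorable occurrence that has the following characteristics". The characteristics include death, threat to life, and "Requires hospitalization (hospital admission for constant observation or prolongs existing hospitalization". The section does not mention the 12.2 list. Sections 12.1 and 12.4 and Appendix 5 require SAEs to reach the ethics committee within 24 hours.

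**Collection schedule.** Ileus and suprafascial haematoma are secondary endpoints in section 8.2 and rows of Table 4. In flowchart 9.10 the ileus row and the "Supra fascial" haematoma row each have one mark, at V3 (up to 72 h after surgery). Section 10.2.2 lists both, with urinary retention, for the first 48 to 72 hours. Section 10.2.3 then gives the day 7-12 visit to the treating physician, "who determines if any of the secondary outcomes described above have occurred".

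**The concern.** Two sets of instructions conflict.

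First, the 12.2 exclusion works by diagnosis and the 12.3 inclusion works by consequence. A suprafascial haematoma that prolongs the stay is on the excluded list of one section and inside the SAE definition of the next. At stake are the 24-hour report and the information that reaches the safety committee. Section 12.6 charges that committee with monitoring AEs, and Appendix 5 ties its decision on stopping the study to AE frequency being above expectation or to an SAE.

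Second, a site that works from the flowchart stops looking for ileus and haematoma at 72 h, while a site that works from 10.2.3 looks again at days 7-12. The by-arm percentages would then partly reflect site practice. Both events are complications of operations that the protocol says differ in the extent of pelvic dissection, and the clinical data are meant to inform a definitive trial (section 3).

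**Working it through.** The plan gives no figure to reproduce, and no arithmetic applies beyond counting flowchart marks. The check sets the sections side by side.

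**1. Does the 12.2 list have a seriousness limit?**
- Ileus, urinary retention, suprafascial haematoma: no limit of any kind.
- Postpartum haemorrhage: a volume limit (2.5 L), but nothing about consequence.
- Pre-existing conditions: limited to those that do not worsen.

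The fifth item shows that the list can carry a proviso about clinical course. The four complications have none.

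**2. Is the list consistent with the rest of section 12?**
- Against 12.2's own general definition: no. Each listed event is an unfavourable sign or condition following a procedure.
- Against 12.3: no, for any case that meets a seriousness criterion. Section 12.3 speaks of any unfavourable occurrence, not of any AE, so on its face it includes listed events with serious consequences.
- Is there a precedence rule? None is stated. Section 12.4 has the investigator reach a diagnosis and record that diagnosis as the adverse event. A site recording a suprafascial haematoma would then find it on the excluded list.

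**3. What does the flowchart collect, and when?** Columns are read as V1, V2, V3, V4, V5, Vn.

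| Item | V3 (to 72 h) | V4 (day 7-12) | V5 (day 42) | Vn |
|---|---|---|---|---|
| Ileus | yes | no | no | no |
| Suprafascial haematoma | yes | no | no | no |
| Complications, reintervention, Near Miss, transfusion, Clavien-Dindo | yes | yes | yes | yes |
| Urinary retention | no row | no row | no row | no row |

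Section 10.2.3 requires the V4 assessment of ileus and haematoma that the flowchart omits. Section 8.2 sets no time limit on either endpoint. The section 15 definitions refer to the postoperative or post-surgical period, also without a 72 h limit. The day-42 telephone script (Appendix 9) asks an open question about problems needing medical attention and names neither event.

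Bringing the two rows into line with the other complication rows takes 2 rows × 3 columns (V4, V5, Vn) = 6 marks. Section 10.2.3 directly supports the two at V4. The other four rest on the 42-day follow-up and the pattern of the neighbouring rows.

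**4. Urinary retention.** It is to be evaluated under 10.2.2, but it has no flowchart row, no section 15 variable and no place among the 8.2 endpoints, and 12.2 excludes it as an AE. No dedicated field records it.

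**The case against.** The strongest reply is that nothing serious is lost. Section 12.3 is worded to cover any unfavourable occurrence, so a serious listed event is already an SAE and must be reported in 24 hours; a site that omits it has misread the protocol. Section 10.2.3 and the open-ended section 15 definitions keep endpoint collection going past 72 h. Re-operation, shock (a Near Miss criterion), postoperative stay and Clavien-Dindo grade are recorded separately. Intraoperative bleeding is recorded in mL whatever the volume, and transfusion of more than 4 red-cell units is itself an AE. Keeping non-serious ileus or haematoma out of AE reporting is a legitimate sponsor choice, since both are collected as endpoints. The study is a descriptive feasibility study of 60 women.

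Most of this stands. A reader might infer from 12.2 and the flowchart that serious cases escape both safety reporting and the endpoint. The documents do not support that, because 12.3 covers such cases on its face and 10.2.3 reopens the endpoint at days 7-12.

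The reply does not remove the contradictions. It assumes that 12.3 overrides 12.2 and that 10.2.3 overrides the flowchart, and the protocol says neither. The flowchart's Adverse Events row does not help, since it depends on the disputed definition. The other rows may record a consequence, but they do not fill the ileus or haematoma lines of Table 4 or by themselves start a 24-hour report. The bleeding variable covers loss during the procedure only.

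**Conclusion.** The point holds as a pair of internal contradictions, and both should be corrected. A site following 12.2 literally could leave out an SAE that 12.3 requires. A site following the flowchart literally could leave out a late ileus or haematoma that 10.2.3 requires. Serious cases can be missed, but do not necessarily escape.

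The size cannot be put as a number of women. The documents give no rate of ileus or haematoma, no share presenting after 72 h and no share that is serious, so any count would rest wholly on invented rates. What can be said is which outputs are exposed: SAE reports for four listed diagnoses, the AE frequency monitored by the safety committee, and two secondary-endpoint rows of Table 4. The analysis of those rows is descriptive, so no hypothesis test is affected.

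The conclusion assumes that the single flowchart mark in each of the two rows belongs to V3, as the table layout shows, and that no site instruction outside the protocol settles precedence. The urinary-retention gap is minor.

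**What to change.** 1. **Section 12.2.** After the list, add: *These events are not reported as AEs unless they meet a criterion of 12.3, in which case they are reported as SAEs.* This keeps the sponsor's choice for non-serious cases and settles precedence.
2. **Flowchart 9.10.** Mark ileus and suprafascial haematoma at V4, to agree with 10.2.3, and at V5 and Vn, in line with the other complication rows and the 42-day follow-up.
3. **Urinary retention (minor).** Add a yes/no variable in section 15 and a flowchart row, or remove it from 10.2.2.

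The cost is one sentence, six flowchart marks and, if retention is kept, one field and one row. The downside is a few more SAE reports and slightly higher stated complication percentages. No clinical rule changes.

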12.3. Definition of serious adverse event (SAE)

Serious adverse event (SAE) is defined as any unfavorable occurrence that has the following characteristics:

- Cause death
- Life-threatening: "Life-threatening" corresponds to situations in which the participant was at risk of death at the time of the event.
- Requires hospitalization (hospital admission for constant observation or prolongs existing hospitalization)
- Causes a significant disability or alteration of a person to perform normal vital functions, persistent or significant disability, does not include events of minor significance such as common headache, nausea, vomiting, diarrhea, flu, accidental trauma that may interfere with normal functions of everyday life and prevent them, but they are not important events.
- Congenital anomaly / birth defect in the participant's offspring.

• Major medical events at the discretion of the principal investigator that may endanger the participant.

12.4.EA and SAE registration:

- The investigator will review all the documentation related to the adverse event and verify that it is consigned in the adverse event report form (Appendix 6).
- The investigator will determine a diagnosis based on symptoms, signs, and all clinical information. The diagnosis is the one that is recorded as an adverse event.
- In the event of serious adverse events, the principal investigator will report them to the institutional ethics committee within the first 24 hours of detecting the adverse event.
- In case of adverse events, the principal investigator will report it to the institutional ethics committee within the first month of detecting the adverse event.

12.5. Assessment of AE intensity:

The researcher will carry out an evaluation of the intensity of each AE and SAE:

Grade 1 or mild: Mild symptoms that cause minimal or no interference with social activities and usual functions with indicated intervention.

Grade 2 or moderate event: Moderate symptoms causing more than minimal interference with usual social and functional activities with indicated intervention.

Grade 3 or serious event: Serious symptoms that cause inability to perform usual social and functional activities with indicated intervention or hospitalization.

Grade 4 or life-threatening event: possibly life-threatening symptoms causing inability to perform basic self-care functions with indicated intervention to prevent permanent failure or ongoing disability or death.

Grade 5 death related to AE.

12.6. Adverse event evaluation and safety committee:

The safety committee will be integrated by:

- Methodologist / statistician: [name]
- Peer evaluator: Obstetrician gynecologist specialized in Intensive Care: [name] [name]

• Obstetrician gynecologist specialized in Epidemiology: [name] [name]

All independent of the group of researchers.

They will be in charge of monitoring the occurrence of AE and the proper conduct of the study.

12.7. Assessment of causality:

The safety committee will determine the probability that the protocol caused the AE. The committee may change its opinion on causation based on AE tracking information. The criteria presented below are intended to serve as a reference:

- Exposure: Proof that the participant was exposed to the product.
- Temporal evaluation: Time since the intervention in relation to the moment of the AE onset.
- Probable cause: Cause that most reasonably explains the occurrence of the AE

12.8. Protection of the safety of the participants:

As part of the management of the previously exposed medical and legal risks, Fundación Valle del Lili, will acquire a civil liability policy to ensure the safety of the participants in the event of an accident or adverse event.

Activity / Year	March- April 2021	May 2021	Agust 2021- September 2023	October 2023- June 2023
1. Protocol writing	Х			
		Approvals		
2. Presentation of the protocol		Х		
3. Methodological evaluation		Х		
4. Evaluation by the FVL ethics committee		Х		
		Execution		
5. Data collection			Х	

6. Analysis of the information			Х
S	Socialization of Results and F	Reports	
7. Manuscript writing			Х
8. Poster presentation			Х
9. Manuscript submission			Х
10. Article publication			Х

